
Statistical Analyses:
	
Analysis of Demographics and Other Baseline Characteristics:
 
Data will be summarized with respect to demographic and baseline characteristics, medical history, immune response measurements, and all safety measurements using descriptive statistics (quantitative data) and contingency tables (qualitative data) for each CVnCoV lot separately, for pooled CVnCoV lots, for placebo and overall.
 
Safety Analyses:
 
Safety endpoints will be described for each CVnCoV lot separately, for pooled lots, for placebo and overall.
 
 
• Solicited AEs:
 
 
The frequencies and percentages of subjects experiencing each solicited local and systemic AE within 7 days after each vaccination will be presented by intensity and overall.
 
 
• Unsolicited AEs:
 
 
Unsolicited AEs including SAEs and AESIs will be coded using the Medical Dictionary for Regulatory Activities (MedDRA) by System Organ Class (SOC) and Preferred Term (PT). The frequency and percentage of subjects reporting at least 1 AE and each unsolicited AE within 28 days after each vaccination and overall will be tabulated at the SOC and PT levels. Additional similar tabulations will be performed to evaluate severity and relationship to trial vaccine.
 
Immunogenicity Analysis:
 
Descriptive statistics for the immunogenicity endpoints will be provided for each CVnCoV lot separately (samples of 200 subjects analyzed), for pooled lots and for 50 subjects of the placebo group on Days 1, 29 and 43..
 
GMCs/Geometric mean titers (GMTs) with 95% confidence interval (CI) will be computed for SARS-CoV-2 RBD of S protein antibody levels and for neutralizing antibodies, overall and separately in subjects seronegative at baseline and in subjects seropositive at baseline. Geometric mean of fold change from baseline will be added for subjects seropositive at baseline.
 
For each readout, seroconversion rates will also be summarized at each blood sampling time point in subjects who are SARS-CoV-2 seronegative at baseline.
 
To assess lot-to-lot consistency descriptively, two-sided 95% CI of the ratio of GMCs of SARS-CoV-2 RBD of S protein antibodies between subjects receiving 2 different lots of CVnCoV will be computed for Day 43.
 
Efficacy Analyses:
 
The attack rates of first episodes of virologically-confirmed COVID-19 of any severity (according to case definition) in CVnCoV (pooled lots) and placebo groups will be computed as well as VE, defined as the percent reduction in the frequency of COVID-19 cases in vaccinated subjects compared with subjects who received placebo with its exact 95% CI as follows:



<math>VE = 1 - RR = 1 - (ARV/ARP) = 1 - (p / r (1-p))</math>
 
where
 
ARV = attack rate in vaccinated groups (pooled lots) = <math>nv/Nv</math> = number of subjects reporting at least 1 COVID-19 episode in the CVnCoV groups / total follow-up time of evaluable subjects in the CVnCoV groups (number of person-month)
 
ARP = attack rate in placebo group = <math>np/Np</math> = number of subjects reporting at least 1 COVID-19 episode in the placebo group / total follow-up time of evaluable subjects in the placebo group (number of person-month)
 
RR = relative risk = <math>ARV/ARP</math>
 
p = proportion of COVID-19 cases coming from the CVnCoV groups (pooled lots) among all cases = <math>nv/(nv+np)</math>
 
r = ratio of total follow-up time of evaluable subjects in the CVnCoV groups (pooled lots) over total follow-up time of evaluable subjects in the placebo group = <math>Nv/Np</math>
 
Similar analyses will be performed to describe the efficacy in the prevention of asymptomatic infections. The number and percentage of subjects reporting at least 1 mild, moderate, severe, and moderate to severe COVID-19 episode will be presented in each group.
 
In order to consider incidence and severity of COVID-19 disease, a VE measure based on the BoD scores (<math>VE_{BoD}</math>) will be derived. <math>VE_{BoD}</math> is defined as the relative reduction in the BoD score in the CVnCoV groups compared to the placebo group and is calculated as 1 minus the relative risk.
 
All efficacy endpoints will be analyzed without success criteria testing.

--

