
Data and Safety Monitoring Board:
	
An independent DSMB will be convened to oversee the safety and efficacy of subjects participating in the trials CV-NCOV-004 and CV-NCOV-005, to assess the progress and conduct of the trials, to review the cumulative safety data from the trials, and to make recommendations to CureVac whether to continue, modify, or stop the trials. The DSMB will have regularly scheduled meetings to perform these responsibilities. During these meetings, the DSMB will be informed of the safety data being generated in other ongoing clinical trials of CVnCoV. In addition to safety data, the DSMB will be asked to review efficacy data at the interim analysis and at other time points during the trial for a continued assessment of the risk-benefit of the trial. As part of the risk-

	
benefit analysis, the DSMB will periodically monitor COVID-19 cases for signals of VDE.
 
The DSMB Charter will describe in detail the composition and objectives of the DSMB; the responsibilities of the DSMB, CureVac and the contract research organization; the schedule and conduct of the DSMB meetings; and the datasets to be reviewed.

Sample Size Justification:
	
HCWs participating to the observational COVID19-5-P-002 trial, other HCWs or students in clinical training will be enrolled. The anticipated sample size is 2,520 subjects. This number of subjects will give the trial more than 80% statistical power to detect AEs that may occur at about 1:1000 incidence.

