## 5.2 Scientific Rationale for Trial Design

See also Sections 3.2 and 5.1.

The difference in appearance and presentation of the investigational CVnCoV vaccine and placebo requires the trial to be conducted in an observer-blinded manner, which is a commonly used and well-accepted method for trial blinding. The randomized, observer-blinded, and placebo-controlled design will reduce the risk of bias in the safety, immunogenicity and efficacy outcomes of the trial (see also Section 7.3).

A total of 3,500-4,000 subjects is aimed to participate in the observational trial COVID19-5-P-002 at the University of Mainz. HCWs participating to the observational trial COVID19-5-P-002 will be invited to participate in the CV-NCOV-005 trial. Pending the number of subjects continuing from the observational trial in the CV-NCOV-005 trial, additional HCWs, and potentially students in clinical training will be recruited for the present trial. Participants of COVID19-5-P-002 who do not join CV-NCOV-005 will continue participation in COVID19-5-P-002.

The primary safety objective is to generate a large-scale safety database that will demonstrate the safety of CVnCoV among HCWs. The safety and reactogenicity of a 2-dose schedule of CVnCoV will be assessed in detail by measuring the frequency and severity of the following AEs: solicited local and systemic reactions for 7 days after each vaccination; unsolicited AEs for 28 days after each vaccination; medically-attended AEs through 6 months after the second trial vaccination; and AESIs and SAEs through 1 year after the second trial vaccination. As such, each subject will participate in the trial for approximately 13 months for the safety follow-up.

The detailed reactogenicity and immunogenicity data generated in Phase 2b of Trial CV-NCOV-004 will be the main dataset to be submitted in support of early conditional approval of CVnCoV. The present trial will provide additional safety and immunogenicity data, in the intended trial population of adults at the selected dose level, to be available for the file to be submitted to obtain early conditional approval in the European Union.

As a secondary efficacy objective, the efficacy of a 2-dose schedule of CVnCoV in the prevention of first episodes of virologically-confirmed cases of COVID-19 of any severity in SARS-CoV-2 naïve subjects will be assessed.

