### **7.3.1 Randomization**

Approximately 2,520 subjects 18 years of age or older will be enrolled at the site at Mainz University, Germany and will be randomized in a 1:1:1 ratio (840 by randomization group) to receive either 1 of 2 different lots of CVnCoV (CVn CoV Lot 1 group and CVnCoV Lot 2 group) or placebo (placebo group). The randomization will be performed centrally and stratified by age group (18 to 60 and  $\geq 61$  years of age). The randomization scheme will be generated and maintained by the Statistical and Data Management group at the contract research organization (CRO), PRA. Subjects will be enrolled into the trial online and randomized using an interactive web response system (IWRS). After demographic and eligibility criteria are entered into the system, subjects enrolled into the trial will be assigned their treatment assignment.

The first 1,260 subjects enrolled are planned to be included in the Immunogenicity/Reactogenicity Subset.

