## 10 STATISTICAL CONSIDERATIONS

### 10.1 Sample Size Determination

#### 10.1.1 Primary Safety Objective

While solicited vaccine reactions are expected, AEs that would limit product development may arise. Table 5 below indicates the probability of observing at least 1 AE in the trial when the true incidence of the AE with CVnCoV is 1:1000, 5:1000 or 1:100.

With a total of 1,680 subjects receiving CVnCoV (840 for each lot), AEs with a true incidence of 1:1000 will likely be observed in this trial with a 81.4% probability of observing at least one. Additionally, observation of 0 AE in 1,680 subjects would be associated with a 95% confidence that the true incidence rate of this AE is below 1.8:1000.

With a total of 840 subjects included in the Immunogenicity/Reactogenicity subset and receiving CVnCoV (420 for each lot), solicited/unsolicited AEs with a true incidence of 5:1000 will likely be observed in this trial with a 98.5% probability of observing at least one. Observation of 0 AE in 840 subjects would be associated with a 95% confidence that the true incidence rate of this AE is below 3.6:1000.

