### 10.3.5 Safety Analysis

No formal statistical testing of safety data is planned.

Safety endpoints will be described for each CVnCoV lot separately, for pooled lots, for placebo and overall.

**Solicited AEs:** The frequencies and percentages of subjects experiencing each solicited local and systemic AE within 7 days after each vaccination will be presented by intensity and overall. For subjects with more than 1 episode of the same AE within 7 days after a vaccination, the maximum intensity will be used for tabulations. Similar tabulations will be performed for solicited systemic AEs by relationship to trial vaccination. Solicited local AEs will be by definition considered as related to the trial vaccine. Time to onset (in days) and duration (in days) will also be summarized for each solicited local and systemic AEs. Summary tables showing the occurrence of at least 1 local or systemic solicited AE within 7 days after each vaccination will also be presented.

**Unsolicited AEs:** Unsolicited AEs including SAEs and AESIs will be coded using the Medical Dictionary for Regulatory Activities (MedDRA) by SOC and PT.

The frequency and percentage of subjects reporting at least 1 unsolicited AE within the 28 days after each vaccination and overall will be tabulated globally and for each SOC and PT levels.

Similar tables will be provided for: related unsolicited AE, Grade 3 or higher unsolicited AE, medically-attended AEs that occur within 6 months after the second trial vaccination, SAE, related SAE, AESI, related AESI, AEs leading to withdrawal or trial discontinuation and SAE resulting in death through 1 year after the second trial vaccination.

When an AE occurs more than once for a subject within the 29 days post 1 vaccination, the maximal severity and strongest relationship to the vaccine group will be counted.

Only AE post first vaccination will be considered in the summary tables. AE starting prior to the first vaccination will only be listed.

Data listings of fatal and SAEs will be provided by subject.

Vital signs will be summarized by descriptive statistics at each visit including change from baseline and a listing will be provided.

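### The synopsis presents as statistical power of 2,520 subjects what is the 81.4% chance of seeing at least one event among 1,680 CVnCoV recipients

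*Protocol*

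**What the plan says.** The synopsis states the total ("The anticipated sample size is 2,520 subjects") and continues: "This number of subjects will give the trial more than 80% statistical power to detect AEs that may occur at about 1:1000 incidence". It names no test, significance level, comparator rate or effect size.

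Protocol 10.1.1 describes the quantity differently: "AEs with a true incidence of 1:1000 will likely be observed in this trial with a 81.4% probability of observing at least one". It ties this to the 1,680 subjects on CVnCoV (840 per lot) and to the incidence among recipients, "when the true incidence of the AE with CVnCoV is 1:1000, 5:1000 or 1:100". It adds that zero events in 1,680 would put the incidence below 1.8:1000 with 95% confidence. Table 5 is titled as a probability of observation. SAP 8.5.1 repeats the table and the wording.

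On analysis, Protocol 10.3.5 says "No formal statistical testing of safety data is planned". Safety endpoints are described by lot, for pooled lots, for placebo and overall. On purpose, Protocol 5.2 says "The primary safety objective is to generate a large-scale safety database that will demonstrate the safety of CVnCoV among HCWs".

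**The concern.** Power is the probability that a stated test rejects a null hypothesis under a stated alternative. This plan has no safety test, so no power is defined, yet the synopsis claims more than 80% of it. It also credits the figure to all 2,520 subjects, a third of whom receive placebo and do not enter the calculation.

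In a randomized, placebo-controlled trial, power to detect AEs is naturally read as power to detect an effect of the vaccine. Someone who reads only the synopsis, alongside the Section 5.2 statement about demonstrating safety, could take the absence of a visible imbalance in a 1:1000 event as an adequately powered negative finding. The design gives no such assurance.

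**Working it through.** **Inputs from the documents.** CVnCoV recipients n = 1,680; placebo n = 840; total 2,520 (Protocol 7.3.1 and 10.1.1). True incidence p = 0.001 (Protocol 10.1.1). No alpha, test or placebo AE rate is given.

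**Step 1: reproduce the plan's figure.** P(at least one event) = 1 − (1 − p)^n.
- n = 1,680: 1 − 0.999^1680 = 0.8138, the stated 81.4%.
- n = 840: 56.8%; n = 420: 34.3%. Both match Table 5, as do its 5:1000 and 1:100 rows.
- Zero-event bound: 1 − 0.05^(1/1680) = 1.78:1000, the stated 1.8:1000.

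**Step 2: test the synopsis attribution.** With n = 2,520, 1 − 0.999^2520 = 0.9196, or 92.0%. The phrase about exceeding 80% therefore describes the 1,680, not the 2,520. The number of recipients needed to pass 80% is ln(0.2)/ln(0.999) = 1,608.6, so 1,609.

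**Step 3: what the criterion responds to.** Its only input is the CVnCoV event count. With no vaccine effect, the chance of at least one event among 1,680 depends on the background rate b (assumed; the documents give none):

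| b | 1 − (1 − b)^1680 |
|---|---|
| 0 | 0% |
| 1:100,000 | 1.7% |
| 1:10,000 | 15% |
| 0.5:1000 | 57% |
| 1:1000 | 81.4% |

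The criterion is informative for events that are almost absent in the background. It does not separate vaccine from background when the background is near 1:1000.

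**Step 4: what a comparison would give, if one were assumed.** Assumptions: Fisher's exact test, two-sided 5%, 1,680 v 840, exact enumeration, counting rejections in the direction of harm only.

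| CVnCoV v placebo | Power |
|---|---|
| 1:1000 v 0 | 0.006% |
| 2:1000 v 1:1000 | 0.33% |
| 5:1000 v 1:1000 | 23% |
| 5:1000 v 0 | 46% |
| 10:1000 v 1:1000 | 84% |

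The first row can be checked by hand. With no placebo events, 8 CVnCoV events give p = 0.058 and 9 give p = 0.034, so 9 are needed. The expected number is 1,680 × 0.001 = 1.68, and P(X ≥ 9) = 0.000065.

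Sensitivity to the assumed test: for 1:1000 v 0, a one-sided 5% test gives 0.04% and a one-sided 2.5% test 0.00%. For 2:1000 v 1:1000, counting rejections in both directions gives 0.68%. The normal approximation gives 7.0% and 6.1% for these two cases, but it is unreliable with so few events.

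**The case against.** The strongest reply is that only one loose sentence is at fault. The sections that govern the analysis call the figure a probability of observing at least one event, state n = 1,680 and pair it with a zero-event bound. Every number reproduces. For a descriptive safety database, that pair is a coherent basis for choosing a size, and leaving placebo out of it is not a design error. No stopping rule, decision rule or conclusion draws on the synopsis sentence. All of this stands, and it limits the point to the synopsis.

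A reader might go further in four ways that the documents do not support.
- *The trial's real power is near zero.* The plan specifies no comparative test, so it has no such power to be near zero. The values in step 4 belong to an assumed test and assumed background rates.
- *The criterion is met just as often when the vaccine does nothing.* This holds only when the background is itself 1:1000, as step 3 shows.
- *Nothing in the safety analysis separates harm from background.* Placebo is tabulated beside pooled CVnCoV (Protocol 10.3.5, SAP 12.6.1). Causality is assessed by investigators (Protocol Appendix 10) who were to be blinded until the later unblinding (Protocol 7.3.2), and related SAEs, AESIs, medically-attended AEs and fatal AEs are tabulated separately (SAP 12.6.1.3).
- *The trial size has no valid justification.* Protocol 10.1.1 and SAP 8.5.1 supply one.

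A further objection is that a risk difference is optional in a descriptive plan and misleading if follow-up differs between arms. The warning is sound: SAP 10.10 censors at unblinding or receipt of an authorized vaccine, and Protocol 8.2 withdraws placebo subjects after unblinding. It restricts where such an interval can be used but does not rule it out.

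**Conclusion.** The synopsis sentence is wrong as written on two counts: it names the wrong quantity (power instead of probability of observation) and the wrong denominator (2,520 instead of 1,680). It also conflicts with the protocol's own Section 10.1.1. This part rests on the documents and on arithmetic that reproduces exactly, with no outside assumption.

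How far a reader could be misled is conditional. Under the assumed Fisher comparison, a 1:1000 AE absent from placebo would be shown as an excess less than 0.1% of the time, and roughly 80% power is reached only at about 10:1000 against 1:1000. This is a wording correction, not a challenge to the sample size or to the descriptive approach to safety.

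**What to change.** **Essential.** Replace the synopsis sentence with: *1,680 CVnCoV recipients give an 81.4% probability of observing at least one AE whose true incidence is 1:1000 (zero events would bound the incidence below 1.8:1000); this is not power to show an excess over placebo.* Protocol 10.1.1, Table 5 and SAP 8.5.1 need no change. The cost is one sentence and a less favourable-sounding claim; no subjects or data are added.

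**Secondary.** In the censored summaries of SAEs, AESIs, medically-attended AEs and fatal AEs (SAP 12.6.1.3), add the pooled CVnCoV minus placebo risk difference with a two-sided 95% score interval, and show follow-up time per arm beside it. The upper limit then tells the reader how large an excess the data cannot exclude. Label it descriptive: no test is planned, and SAP 6.0 records that version 4.0 was written by an unblinded team. Do not apply it to the uncensored repeats in SAP 12.6.1.4 and 12.6.7, where placebo withdrawal and authorized vaccination make the arms' follow-up unequal. The cost is a few columns in tables that are already planned.

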## 2 SCHEDULE OF ACTIVITIES

Subjects that received placebo in the trial following unblinding, will move from their initial schedule of activities (Table 1 or 2) to the End of Trial Visit (Table 2).

Subjects that, following unblinding, receive an authorized vaccine after having received at least one dose of CVnCoV will move to Table 2.

**Table 1 Schedule of Trial Assessments and Procedures for Immunogenicity/Reactogenicity Subset**

**Immunogenicity/Reactogenicity Subset (n=1,260)**

First 1,260 subjects enrolled	Vaccination Period						Follow-up Period			End of Trial
	Clinic Visit	Phone Call	Clinic Visit	Phone Call	Clinic Visit		Clinic Visit		Phone Call	Clinic Visit
Clinic Visit Number	1 a	-	2	-	3	4	5	6	-	7
Visit Window (days)	n/a	-0/+0	-3/+7	-0/+0	-3/+3	-3/+7	-7/+7	-7/+7	-7/+7	-0/+21
Trial Day	1	2	29	30	43	57	120	211	302	393
Vaccination Day (Reference for post-vaccination time points)	-	1	1	29	29+14	29+28	29+91	29+182	29+273	29+364
Visit Week (Wk) / Month (M)			Wk 4		Wk 6	Wk 8	M 4	M 7	M 10	M 13
Signed informed consent	X									
Inclusion/exclusion criteria	X									
Demographics	X									
Medical history	X									
Medication/vaccination history b	X									
Urine pregnancy test c	X		X							
Trial Vaccination										
Review criteria for delay or cancellation of trial vaccination d	X		X							

First 1,260 subjects enrolled	Vaccination Period						Follow-up Period			End of Trial
	Clinic Visit	Phone Call	Clinic Visit	Phone Call	Clinic Visit		Clinic Visit		Phone Call	Clinic Visit
Clinic Visit Number	1 a	-	2	-	3	4	5	6	-	7
Visit Window (days)	n/a	-0/+0	-3/+7	-0/+0	-3/+3	-3/+7	-7/+7	-7/+7	-7/+7	-0/+21
Trial Day	1	2	29	30	43	57	120	211	302	393
Vaccination Day (Reference for post-vaccination time points)	-	1	1	29	29+14	29+28	29+91	29+182	29+273	29+364
Visit Week (Wk) / Month (M)			Wk 4		Wk 6	Wk 8	M 4	M 7	M 10	M 13
Administration of CVnCoV or placebo (observer-blinded administration)	X		X							
Safety Monitoring										
Physical examination e	X									X
Symptom-directed physical examination e			X		X	X	X	X		
Vital signs e,f	X f		X f		X	X	X	X		X
eDiary collection of solicited local and systemic reaction data, and unsolicited AEs g	X	X	X	X	X	X				
Collection of following AEs through the eDiary h :										
• Medically-attended AEs	X	X	X	X	X	X	X	X		
• SAEs and AESIs	X	X	X	X	X	X	X	X	X	X
• AEs leading to vaccine withdrawal or trial discontinuation	X	X	X	X	X	X	X	X	X	X
• Concomitant medication/vaccination	X	X	X	X	X	X	X	X	X	X
COVID-19 Case Detection										
Case detection and collection of case information i	X	X	X	X	X	X	X	X	X	X
Antibody Testingj										
Binding ant body to RBD of S (sp ke) protein of SARS-CoV-2 (~6 mL blood) k	X j		X j		X	X	X	X		
SARS-CoV-2 viral neutralizing activity (~6 mL blood) k	X j		X j		X	X	X	X		
Binding ant body to the N (nucleocapsid) protein of SARS-CoV-2 (~6 mL blood) k	X j				X			X		

First 1,260 subjects enrolled	Vaccination Period					Follow-up Period			End of Trial	
	Clinic Visit	Phone Call	Clinic Visit	Phone Call	Clinic Visit		Clinic Visit		Phone Call	Clinic Visit
Clinic Visit Number	1 a	-	2	-	3	4	5	6	-	7
Visit Window (days)	n/a	-0/+0	-3/+7	-0/+0	-3/+3	-3/+7	-7/+7	-7/+7	-7/+7	-0/+21
Trial Day	1	2	29	30	43	57	120	211	302	393
Vaccination Day (Reference for post-vaccination time points)	-	1	1	29	29+14	29+28	29+91	29+182	29+273	29+364
Visit Week (Wk) / Month (M)			Wk 4		Wk 6	Wk 8	M 4	M 7	M 10	M 13
Cell-mediated Immunity (CMI Subset n=120)										
In a subset of subjects: cell-mediated immunity (~38 mL blood)	X i		X i		X	X	X	X		
Maximum blood volume collected by visit (mL)l	56		50		56	50	50	56		
Trial End										X

AE: adverse event; AESI: adverse event of special interest; SAE: serious adverse event.

- a. Procedures to establish subject eligibility may be performed within 21 days prior to trial vaccine administration, unless otherwise indicated. If all information to establish eligibility is available, these procedures can be done on the same day as trial vaccine administration. Eligibility criteria should be reviewed and confirmed prior to trial vaccine administration.
- b. Medication/vaccination history taken within 6 months prior to enrollment should be recorded to establish eligibility.
- c. A urine pregnancy test will be performed within 24h prior to vaccination before each trial vaccination on Day 1 and Day 29 for women of childbearing potential.
- d. See Section 6.3 and Section 8.1 for an overview of the criteria leading to delay or cancellation of vaccine administration. In case of delay, the vaccination should take place within the allowed time windows, if feasible. The reasons for delay or cancellation should be documented in the subject chart.
- e. Physical examination and vital signs must be performed/measured by a qualified healthcare professional. See Section 9.3.6 for an overview of the required assessments.
- f. Vital signs will be measured pre- and post-vaccination prior to discharge. Subjects will be observed for at least 30 minutes following each vaccination. Vital signs must be within normal or clinically non-relevant abnormal ranges or have returned to pre-vaccination values for the subject to be discharged.
- g. eDiary (electronic diary) for recording of post-vaccination solicited AEs will be provided to subjects as needed. Subjects should be trained on the use of the eDiary. Solicited local and systemic AEs occurring on the day of vaccination (Day 1 and Day 29) and for the following 7 days will be recorded by the subject in the eDiary. In addition, the eDiary will serve as a memory aid for the subject to report unsolicited AEs occurring on the day of vaccination (Day 1 and Day 29) and for the following 28 days. The data will be reviewed with the subject by trial staff at the site visits on Day 29, Day 43, and Day 57. During phone calls, the subject's general well-being will be checked and the subject should be reminded to complete the safety information by eDiary. If the subject reports by phone any concerning local or systemic reactions, or other AEs (e.g., on Day 2 or Day 30), these should be followed-up either by a phone call(s) or by an unscheduled site visit, based on the judgment of the Investigator.

- h. The eDiary will serve as a memory aid for the subject to report the following AEs during the safety follow-up. Subjects should be trained on the use of the eDiary. Medically-attended AEs will be collected through 6 months after the second trial vaccination. Medically-attended AEs are defined as AEs with medically-attended visits that are not routine visits for physical examination or vaccination, such as visits for hospitalization, an emergency room visit, or an otherwise unscheduled visit to or from medical personnel (medical doctor) for any reason. SAEs, AESIs, and AEs leading to vaccine withdrawal or trial discontinuation will be collected through 1 year after the second trial vaccination. During all site visits and phone calls, trial staff will remind subjects to call the site immediately to report the following: if he/she experiences any concerning medical event; any medically-attended visits that are not routine visits for physical examination or vaccination, such as visits for hospitalization, an emergency room visit, or an otherwise unscheduled visit to or from medical personnel (medical doctor) for any reason; or experience a serious medical event, have a change in overall health or be diagnosed with a new medical condition by a doctor. These should be reported regardless of the perceived relationship between the event and the trial vaccine.
- i. During all site visits (except the End of Trial visit) and phone calls, trial staff will remind subjects to contact the site if they have any of the symptoms suggestive of COVID-19. In addition, subjects will be messaged up to twice a week basis to provide a yes or no response to having COVID-19 symptoms. Those who respond “yes” will be contacted by trial staff for follow-up information, if the investigator considers the symptoms could potentially indicate a COVID-19 case, and the process outlined in Section 9.2.1 should be followed. At the End of Trial visit, symptoms suggestive of COVID-19 or any confirmed COVID-19 case will be recorded.
- j. Blood samples should be collected prior to trial vaccination on Day 1 and Day 29.
- k. Binding antibodies to the RBD (receptor-binding domain) of the S (spike) protein and to the N (nucleocapsid) protein of SARS-CoV-2 will be measured by immunoassay. Viral neutralizing antibodies directed against SARS-CoV-2 will be measured by a functional activity assay. The N protein is not a component of the CVnCoV vaccine, but is being measured to determine serostatus of subjects to the SARS-CoV-2 virus (naïve or non-naïve to SARS-CoV-2); distinguish immune responses elicited by infection with SARS-CoV-2 from those induced by CVnCoV vaccination; and determine the occurrence of SARS-CoV-2 infection during the trial.
- l. Blood will be collected for measurement of antibody responses on Days 1, 29, 43, 57, 120 and 211, and cell-mediated immunity on Days 1, 29, 43, 57, 120, and 211 for a total volume of up to 318 mL.

**Table 2 Schedule of Trial Assessments and Procedures for All Other Subjects and for Subjects who, Following Unblinding, Receive an Authorized Vaccine After Having Received at least One Dose of CVnCoV**

(n=1,260)

	Vaccination Period				Follow-up Period			End of Trial
	Clinic Visit			Phone Call	Phone Call	Clinic Visit	Phone Call ii	Clinic Visit
Clinic Visit Number	1 a	2	3	-	-	4	-	5
Visit Window (days)	n/a	-3/+7	-3/+3	-3/+7	-7/+7	-7/+7	-7/+7	-0/+21
Trial Day	1	29	43	57	120	211	302	393
Vaccination Day (Reference for post-vaccination time points)	-	1	29+14	29+28	29+91	29+182	29+273	29+364
Visit Week (Wk) / Month (M)		Wk 4	Wk 6	Wk 8	M 4	M 7	M 10	M 13
Signed informed consent	X							
Inclusion/exclusion criteria	X							
Demographics	X							
Medical history	X							
Medication/vaccination history b	X							
Urine pregnancy test c	X	X						
Trial Vaccination								
Review criteria for delay or cancellation of trial vaccination d	X	X						
Administration of CVnCoV or control vaccine (observer-blinded)	X	X						
Safety Monitoring								
Physical examination e	X							X
Symptom-directed physical examination e		X	X			X		
Vital signs e,f	X f	X f	X			X		X
Collection of following AEs through the eDiary g :								
• Medically-attended AEs	X	X	X	X	X	X		

	Vaccination Period				Follow-up Period			End of Trial
	Clinic Visit			Phone Call	Phone Call	Clinic Visit	Phone Call i	Clinic Visit
Clinic Visit Number	1 a	2	3	-	-	4	-	5
Visit Window (days)	n/a	-3/+7	-3/+3	-3/+7	-7/+7	-7/+7	-7/+7	-0/+21
Trial Day	1	29	43	57	120	211	302	393
Vaccination Day (Reference for post-vaccination time points)	-	1	29+14	29+28	29+91	29+182	29+273	29+364
Visit Week (Wk) / Month (M)		Wk 4	Wk 6	Wk 8	M 4	M 7	M 10	M 13
• SAEs and AESIs	X	X	X	X	X	X	X	X
• AEs leading to vaccine withdrawal or trial discontinuation	X	X	X	X	X	X	X	X
Concomitant medication/vaccination	X	X	X	X	X	X	X	X
COVID-19 Case Detection								
Case detection and collection of case information h	X	X	X	X	X	X	X	X
Antibody Testing								
Binding antibody to the N (nucleocapsid) protein and of SARS-CoV-2 i (~6mL blood)	X i		X			X		
Maximum blood volume collected by visit (mL)	6		6			6		
Trial End								X

AE: adverse event; AESI: adverse event of special interest; SAE: serious adverse event.

- Procedures to establish subject eligibility may be performed within 21 days prior to trial vaccine administration, unless otherwise indicated. If all information to establish eligibility is available, these procedures can be done on the same day as trial vaccine administration. Eligibility criteria should be reviewed and confirmed prior to trial vaccine administration.
- Medication/vaccination history taken within 6 months prior to enrollment should be recorded to establish eligibility.
- A urine pregnancy test will be performed within 24h prior to vaccination before each trial vaccination on Day 1 and Day 29 for women of childbearing potential.
- See Section 6.3 and Section 8.1 for an overview of the criteria leading to delay or cancellation of vaccine administration. In case of delay, the vaccination should take place within the allowed time windows, if feasible. The reasons for delay or cancellation should be documented in the subject chart.
- Physical examination and vital signs must be performed/measured by a qualified healthcare professional. See Section 9.3.6 for an overview of the required assessments.

- f. Vital signs will be measured pre- and post-vaccination prior to discharge. Subjects will be observed for at least 30 minutes following each vaccination. Vital signs must be within normal or clinically non-relevant abnormal ranges or have returned to pre-vaccination values for the subject to be discharged.
- g. The eDiary will serve as a memory aid for the subject to report the following AEs during the safety follow-up. Subjects should be trained on the use of the eDiary. Medically-attended AEs will be collected through 6 months after the second trial vaccination. Medically-attended AEs are defined as adverse events with medically-attended visits that are not routine visits for physical examination or vaccination, such as visits for hospitalization, an emergency room visit, or an otherwise unscheduled visit to or from medical personnel (medical doctor) for any reason. SAEs, AESIs, and AEs leading to vaccine withdrawal or trial discontinuation will be collected through 1 year after the second trial vaccination. During all site visits and phone calls, trial staff will remind subjects to call the site immediately to report the following: if he/she experiences any concerning medical event; any medically-attended visits that are not routine visits for physical examination or vaccination, such as visits for hospitalization, an emergency room visit, or an otherwise unscheduled visit to or from medical personnel (medical doctor) for any reason; or experience a serious medical event, have a change in overall health or be diagnosed with a new medical condition by a doctor. These should be reported regardless of the perceived relationship between the event and the trial vaccine.
- h. During all site visits (except the End of Trial visit) and phone calls, trial staff will remind subjects to contact the site if they have any of the symptoms suggestive of COVID-19. In addition, subjects will be messaged up to twice a week basis to provide a yes or no response to having COVID-19 symptoms. Those who respond “yes” will be contacted by trial staff for follow-up information, if the investigator considers the symptoms could potentially indicate a COVID-19 case, and the process outlined in Section 9.2.1 should be followed. At the End of Trial visit, symptoms suggestive of COVID-19 or any confirmed COVID-19 case will be recorded.
- i. Binding antibodies to the N (nucleocapsid) protein of SARS-CoV-2 will be measured by immunoassay. The N protein is not a component of the CVnCoV vaccine, but is being measured to determine serostatus of subjects to the SARS-CoV-2 virus (naïve or non-naïve to SARS-CoV-2) and the occurrence of SARS-CoV-2 infection during the trial. The baseline blood sample should be collected prior to trial vaccination on Day 1.
- j. After implementation of protocols version 3 and 4 no longer to be performed in placebo subjects.

